#### 10.4.7 Guidelines for reporting product complaints (IMP)

Any defect in the IMP must be reported as soon as possible by the Investigator to the monitoring team that will complete a product complaint form within required timelines.

Appropriate information (eg, samples, labels or documents like pictures or photocopies) related to product identification and to the potential deficiencies may need to be gathered. The Investigator will assess whether or not the quality issue has to be reported together with an AE or SAE.

**Table 1 - Summary of adverse event reporting instructions**

Event category	Reporting timeframe	Specific events in this category	Case Report Form completion		
			AE form	Safety Complementary Form	Other specific forms
Adverse Event (non-SAE, non-AESI)	Routine	Any AE that is not SAE or AESI	Yes	No	No
Serious Adverse Event (non-AESI or AESI)	Expedited (within 24 hours)	Any AE meeting seriousness criterion per Section 10.4.1.2	Yes	Yes	No
Adverse Event of Special Interest	Expedited (within 24 hours)	Pregnancy	Yes	Yes	Yes
		Symptomatic overdose	Yes	Yes	No

#### 10.5 OBLIGATIONS OF THE SPONSOR

During the course of the study, the Sponsor will report in an expedited manner:

- All SAEs that are both unexpected and at least reasonably related to the IMP (SUSAR), to the regulatory authorities, independent ethics committee (IRB/IEC) as appropriate and to the Investigators.
- All SAEs that are expected and at least reasonably related to the IMPs to the regulatory authorities, according to local regulations.

- The AESIs (listed in section 10.4.5) to those regulatory authorities who require such reporting.

In this study, some AEs are considered related to the underlying condition and thus will not be considered unexpected. RA flares are not considered as AEs. Any other AE not listed as an expected event in the summary of product characteristics or in this protocol will be considered unexpected.

The Sponsor will report all safety observations made during the conduct of the trial in the clinical study report.

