#### **10.1.4 .Assessments during the LTE period (Visit LTE1 and Visit LTE2)**

All the patients who will complete the 6-month-core period are allowed to enter the LTE period in order to continue the treatment with sarilumab (as monotherapy or in combination) for a maximum of another 24 weeks or until the commercial availability of sarilumab in France

All assessments must be performed on the day of the specified visit (see details in Section 1.2). For local laboratory tests required at a given visit (results should be available at this study time-point), a time window of 3 days prior the visit is allowed.

The investigator or designee will:

- Record vital signs.
- For female patients of child-bearing potential performed a urine pregnancy test. If the urine test is positive it must be confirmed by a serum pregnancy test.
- Record the results of hematology, serum chemistry, and fasting lipids results
- Review concomitant medications
- Assess IMP compliance / review patient diary
- Inquire about and record any adverse events/SAEs.

- Deliver IMP for the next study period
- Schedule an appointment for the next visit.

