## 10.4 OBLIGATION OF THE INVESTIGATOR REGARDING SAFETY REPORTING

### 10.4.1 Definitions of adverse events

#### 10.4.1.1 Adverse event

An **adverse event** (AE) is any untoward medical occurrence in a patient or clinical investigation patient administered a pharmaceutical product and which does not necessarily have to have a causal relationship with this treatment.

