#### 10.4.1.2 Serious adverse event

A **serious adverse event** (SAE) is any untoward medical occurrence that at any dose:

- Results in death, or
- Is life-threatening, or  
Note: The term “life-threatening” in the definition of “serious” refers to an event in which the patient was at risk of death at the time of the event; it does not refer to an event which hypothetically might have caused death if it were more severe.
- Requires inpatient hospitalization or prolongation of existing hospitalization, or
- Results in persistent or significant disability/incapacity, or
- Is a congenital anomaly/birth defect
- Is a medically important event  
Medical and scientific judgment should be exercised in deciding whether expedited reporting is appropriate in other situations, such as important medical events that may not be immediately life-threatening or result in death or hospitalization but may jeopardize the patient or may require medical or surgical intervention (ie, specific measures or corrective treatment) to prevent one of the other outcomes listed in the definition above.

Note: The following list of medically important events is intended to serve as a guideline for determining which condition has to be considered a medically important event. The list is not intended to be exhaustive:

- Intensive treatment in an emergency room or at home for:
  - Allergic bronchospasm
  - Blood dyscrasias (ie, agranulocytosis, aplastic anemia, bone marrow aplasia, myelodysplasia, pancytopenia, etc.),
  - Convulsions (seizures, epilepsy, epileptic fit, absence, etc.).
- Development of drug dependence or drug abuse
- ALT >3 x ULN + total bilirubin >2 x ULN or asymptomatic ALT increase >10 x ULN
- Suicide attempt or any event suggestive of suicidality

- Syncope, loss of consciousness (except if documented as a consequence of blood sampling)
- Bullous cutaneous eruptions
- Cancers diagnosed during the study or aggravated during the study
- Chronic neurodegenerative diseases (newly diagnosed) or aggravated during the study
- Suspected transmission of an infectious agent.

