#### **10.4.2 Serious adverse events waived from expedited regulatory reporting to regulatory authorities**

Not applicable.

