#### **10.4.3 General guidelines for reporting adverse events**

- All AEs, regardless of seriousness or relationship to IMP, spanning from the signature of the informed consent form until the end of the study as defined by the protocol for that patient, are to be recorded on the corresponding page(s) or screen(s) of the eCRF.

- Whenever possible, diagnosis or single syndrome should be reported instead of symptoms. The Investigator should specify the date of onset, intensity, action taken with respect to IMP, corrective treatment/therapy given, additional investigations performed, outcome, and his/her opinion as to whether there is a reasonable possibility that the AE was caused by the IMP or by the study procedure(s).
- The Investigator should take appropriate measures to follow all AEs until clinical recovery is complete and laboratory results have returned to normal, or until progression has been stabilized, or until death, in order to ensure the safety of the patients. This may imply that observations will continue beyond the last planned visit per protocol, and that additional investigations may be requested by the monitoring team up to as noticed by the Sponsor.
- When treatment is prematurely discontinued, the patient's observations will continue until the end of the study as defined by the protocol for that patient.
- Laboratory, vital signs or ECG abnormalities are to be recorded as AEs only if:
  - Symptomatic and/or
  - Requiring either corrective treatment or consultation, and/or
  - Leading to IMP discontinuation or modification of dosing, and/or
  - Fulfilling a seriousness criterion, and/or
  - Defined as an AESI.

Instructions for AE reporting are summarized in Table 1.

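### Protocol 10.5 says RA flares are not adverse events while 10.4 makes no exception, so a flare that meets a seriousness criterion may go unreported or be classified differently between sites

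*Protocol*

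**What the plan says.** Protocol 10.5, on the sponsor's reporting obligations, states that "RA flares are not considered as AEs". It does not define a flare, does not address a flare that meets a seriousness criterion, and names no other form on which to record one.

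The sections addressed to investigators read differently:

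- 10.4.1.1 defines an AE as "any untoward medical occurrence in a patient or clinical investigation patient administered a pharmaceutical product", with no exception for the disease under study.
- 10.4.1.2 lists among the seriousness criteria "Requires inpatient hospitalization or prolongation of existing hospitalization", again without exception.
- 10.4.2, headed "Serious adverse events waived from expedited regulatory reporting to regulatory authorities", is marked as not applicable, so nothing is waived.
- 10.4.3 requires the recording of "All AEs, regardless of seriousness or relationship to IMP, spanning from the signature of the informed consent form until the end of the study".
- Table 1 describes the events in the SAE row as "Any AE meeting seriousness criterion per Section 10.4.1.2".

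AE and SAE incidence is a stated safety endpoint for both the core and the extension periods (Clinical Trial Summary, Endpoints). SAP 5.1.4 and 5.3.2.4 analyse the AEs that were recorded and contain no rule, listing or table for flares.

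At the extension visits, Protocol 10.1.4 instructs the site to "Inquire about and record any adverse events/SAEs" and schedules no PRO, DAS28-ESR, CDAI or joint count.

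**The concern.** The same event has two incompatible classifications in one protocol. A site that works from 10.4 reports an admission for a flare as an SAE within 24 hours. A site that takes 10.5 at its word does not record it as an AE, and through Table 1 it never reaches the SAE row. Each can cite the protocol.

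The SAE count then depends partly on which section a site follows, and any error goes one way: events can be left out, and none are added. Nothing in the SAP can recover an event that was not recorded.

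The point matters most in the extension. Its only stated objective is safety (Protocol 5.3; SAP 1.2.3), and AE reporting is the main route by which a flare could become visible there.

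**Working it through.** No figure in the plan needs reproducing. The check is a cross-reading in four steps.

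**1. Classify one event under each section.** Take a patient on study who is admitted to hospital for an RA flare.

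| Section | Result |
|---|---|
| 10.4.1.1 | AE: an untoward medical occurrence, no exception |
| 10.4.1.2 | SAE: admission criterion met, no exception |
| 10.4.2 | Not waived |
| 10.4.3 | Recorded in the eCRF |
| 10.4.4 | As an SAE, entered within 24 hours |
| 10.5 | Not an AE |
| Table 1, read with 10.5 | Not in the SAE row, because that row requires an AE |

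**2. Look for a tie-breaker inside 10.5.** The sentence before the flare statement concerns AEs linked to the underlying disease and says they will not count as unexpected, so it still treats them as AEs. The sentence after it deals with the expectedness of other AEs, as though flares were among the AEs just discussed. The paragraph therefore looks like an expectedness rule, but the flare sentence itself takes flares out of the AE category altogether. The context suggests one intention and the words state another.

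**3. Check what else would show the event in the extension.** The extension lasts up to 24 of at most 48 treatment weeks (24/48 = 50%) and has two scheduled visits.

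- RAID, other PROs, DAS28-ESR, CDAI and joint counts are not scheduled at LTE1 or LTE2 (Protocol 10.1 and 10.1.4; SAP 1.5 flow chart).
- An early-withdrawal visit collects all of these and the reason for leaving (Protocol 10.1.5), and SAP 5.3.1 tabulates treatment inefficacy as a withdrawal reason. This helps only if the patient leaves the study.
- Concomitant medication is recorded with the reason for giving it (Protocol 8.8), but SAP 5.3.2.4 tabulates it by therapeutic class, not by reason.
- ESR belongs to the hematology panel (Protocol 1.2, footnote i), which is drawn at LTE1 and LTE2. However, the hematology list in SAP 5.1.4 omits ESR, and SAP 5.1.3 lists it only as a core-period endpoint.

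A flare in a patient who stays in the extension, even one needing admission, can therefore reach no planned table that identifies it as a flare.

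**4. Size.** Let *f* be the number of patients whose only SAE is an unreported flare, and *N* the safety population. The SAE incidence is understated by *f/N*. If all 140 planned patients are treated, each such patient lowers it by 1/140 = 0.7 percentage points. The documents give no value for *f*, no flare rate and no expected SAE incidence. Extension exposure is also unknown, since entry depends on sarilumab not yet being commercially available in France (Protocol 7.3). The total effect cannot be computed.

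**The case against.** The strongest defence is that the flare sentence sits in the sponsor's section, in a paragraph on expectedness, and does not govern investigators. Section 10.4.1.2 defines an SAE directly as an untoward medical occurrence, not as a kind of AE, so an admission for a flare qualifies without passing through the AE label. Section 10.4.4 then requires prompt entry, and Table 1 only summarises these instructions. This stands as far as it goes. A reader might infer that every hospitalised flare is lost from the safety data; the documents do not support that, because 10.4 still gives investigators every reason to report it. What remains is that it may be lost or handled inconsistently.

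A reader might also infer that nothing else in the extension captures a flare. That goes too far: the early-withdrawal visit, the inefficacy withdrawal reason, the medication record and ESR all leave some trace. The gap is limited to scheduled disease-activity and PRO assessments in patients who remain.

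Nor does the gap extend to treatment interruptions in the core period. Scheduled assessments continue at W4, W12 and W24 (10.1.3), and 10.3.4 continues follow-up after permanent discontinuation.

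Finally, treating worsening of the studied disease as an efficacy matter is a coherent choice. Protocol 11.4.2.1 already does so for glucocorticoid escalation, and an extension with only a safety objective need not schedule efficacy scores. That defends leaving non-serious flares out of the AE tables. It does not resolve how to classify a flare that meets a seriousness criterion.

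**Conclusion.** The contradiction is real and affects a stated safety endpoint. Section 10.5 cannot be reconciled with 10.4.1.1, 10.4.1.2 and 10.4.3 as written, and Table 1 can be read in a way that excludes a serious flare from SAE reporting. The supportable conclusion is that such a flare may go unreported or be classified differently between sites, with a possible downward bias in SAE incidence. In a patient who stays in the extension, no scheduled disease-activity or PRO assessment would show it.

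The direction assumes that at least some sites apply 10.5 literally; if none do, nothing is lost. A percentage undercount would rest entirely on assumed flare and SAE rates that appear nowhere in the documents, so none is offered. The primary endpoint is unaffected and the study is descriptive (Protocol 11.4.2.3). The point should still be corrected, because the remedy is cheap and an unrecorded event cannot be recovered at analysis.

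**What to change.** Reconcile Protocol 10.5 with 10.4.1.1, 10.4.1.2, 10.4.3 and Table 1. State that any flare meeting a seriousness criterion is recorded and counted as an SAE in all study periods, and that it may be treated as expected for regulatory reporting, which appears to be the purpose of that paragraph.

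In SAP 5.3.2.4, tabulate SAEs with and without flares, using a single term or flag so that the split can be programmed. The split works only on recorded events, so the protocol clarification has to come first.

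Non-serious flares can stay outside the AE tables if that is the sponsor's choice, provided the rule is the same in every period. Recording them as AEs only in the extension and post-treatment period would give the core and extension periods different AE definitions.

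The cost is one clarifying sentence, one additional table split, a few more SAE forms and a slightly higher reported SAE rate. No visit, assessment or treatment rule changes.

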## 10.6 SAFETY INSTRUCTIONS

Please refer to serious adverse events reporting (see Section 10.4.4), adverse event of special interest (see Section 10.4.5) definitions and reporting, and guidelines for management of specific laboratory abnormalities (Section 10.4.6).

### Infections

Biologics including sarilumab have been associated with an increased risk of infections. Physicians should then exercise caution when considering the use of sarilumab in patients with a history of recurring infections or with underlying conditions (e.g., diabetes mellitus) which may predispose patients to infections. Sarilumab should not be administered in patients with active infection. Therefore patients with active current infection or a history of recurring infection (including but not limited to active TB or history of incompletely treated TB and atypical mycobacterial disease, hepatitis B and C, and herpes zoster) will be excluded from the study.

The effects of sarilumab on acute reactants, neutrophils, and the signs and symptoms of infection should be considered when evaluating a patient for a potential infection. Any infection should be reported by the Investigator as an adverse event and a corresponding eCRF form should be filled in (type of infection, treatment with antibiotics if any with route of administration).

As all biologics, sarilumab may induce immunosuppression, increasing the risk of reactivation of latent TB. As a precautionary measure, patients with active TB will be excluded from the study. For inclusion, patient with a past history of TB could be included only if there is a documented confirmation medically validated by the Investigator that the patient was adequately treated and does not meet any of the TB-related exclusion criteria, notably based on physical examination, negative chest X-ray and TB test over the Screening period.

**NOTE:** in case of latent TB infection the patient may be included if a subsequent appropriate anti TB treatment is initiated since at least 3 weeks

## **Systemic hypersensitivity reactions/anaphylaxis**

As infrequent, mild-moderate, systemic hypersensitivity reactions have been observed with sarilumab, the patient should be monitored for 30 minutes after the IMP injection when given at the study site. Also patient should be advised, when IMP is administered at home, to self-monitor for potential signs and symptoms that may suggest a hypersensitive reaction for 30 minutes after administration. Any problems should be documented in the patient's Home Dosing Diary or in the medical notes and reported as AE. In case of systemic hypersensitivity reaction, the IMP should be discontinued and those events meeting seriousness criteria (e.g., hospitalization, life threatening, etc.; see Section 10.4.1.2) should be reported as SAEs.

Signs of a possible hypersensitivity reaction include but are not limited to:

- Fever, chills, pruritus, urticaria, angioedema, and skin rash.
- Cardiopulmonary reactions, including chest pain, dyspnea, hypotension, or hypertension.

If clinical criteria for anaphylaxis are met, appropriate treatment should be administered immediately and the event should be reported as a SAE.

## **Diverticulitis and gastrointestinal perforation**

Symptomatic diverticulosis, diverticulitis, or chronic ulcerative lower GI disease such as Crohn's disease, ulcerative colitis, or other chronic lower GI conditions might predispose to perforations. Therefore patients with a history of previous gastrointestinal perforation or diverticulitis will be excluded from the study.

The Investigator should pay particular attention to gastrointestinal symptoms such as, but not limited to, abdominal pain, hemorrhage, or unexplained change in bowel habits with fever to assure that the diagnosis is not missed and that the conditions are managed appropriately to avoid the complication of perforation. If necessary, the patient should be referred to a specialist. Corticosteroid use is known to increase the risk of gastrointestinal perforations. The Investigator should be aware of this potential risk and monitor any sign of diverticulitis.

Gastro-intestinal perforation is an AESI with immediate notification to be reported as SAE (see Section 10.4.4). Confirmed diverticulitis or gastrointestinal ulceration should be reported as AEs.

## **Management of dyslipidemia**

Patients treated with sarilumab have been observed to have increased elevations of all lipid parameters, and RA is a known independent risk factor for cardiovascular events. Therefore, as a precautionary measure, patients with severe uncontrolled fasting hypercholesterolemia (>3.5 g/L [9.1 mmol/L]) or hypertriglyceridemia (>5.00 g/L [5.6 mmol/L]) will be excluded from the study.

Patients who are found to have dyslipidemia during the course of the study should be treated according to the National Cholesterol Education Program (NCEP)/Adult Treatment Panel 3 (ATP3; See Appendix C) or applicable local guideline. Also see Section 8.8.2 under concomitant medication rules for lipid-lowering therapy.

### **Local injection site reactions**

In previous clinical trials, no clinically significant injection site reactions (ISRs) were observed. Local ISRs, including but not limited, to erythema, induration, pain, and SC emphysema, should be reported as an AE, with the event term recorded in AE eCRF as the symptom followed by 'at injection site' (i.e. 'erythema at injection site'). If needed, ISRs should be treated topically and the treatment(s) should be reported in the eCRF.

## **10.7 ADVERSE EVENTS MONITORING**

All events will be managed and reported in compliance with all applicable regulations, and included in the final clinical study report.

## 11 STATISTICAL CONSIDERATIONS

### 11.1 DETERMINATION OF SAMPLE SIZE

The primary study objective is to assess the change in RAID score from baseline to W24. A sufficient precision (half-length of the 95% confidence interval) is required. According to the literature (44, 45, 46) and findings from the MONARCH and TARGET studies (22, 33), the standard deviation (SD) of the RAID score could be estimated at 2.5 points. On this basis, a sample size of 140 patients (122 evaluable, if 20% non-evaluable patients) produces a precision, two-sided 95% confidence interval (CI), with a distance from the mean to the limits that will be less than 0.5 when the estimated SD is 2.5. Table below gives the 95% CI of change from baseline to W24 of RAID score with this precision (0.44), assuming that the change from baseline will be from 30% to 50% (MCII defined by Dougados in 2012; 47) of baseline score.

Expected change from baseline to W24 of RAID score (Relative to baseline %)	RAID score at Baseline	Expected change from baseline to W24 of RAID score (Absolute value)	95% CI (precision =0.5)
30%	65	2,0	[1,5 ; 2,5]
	5	1,5	[1,0 ; 2,0]
	3,5	1,1	[0,6 ; 1,6]
50%	6,5	3,3	[2,8 ; 3,8]
	5	2,5	[2,0 ; 3,0]
	3,5	1,8	[1,3 ; 2,3]

*Note that on MONARCH study (22), the % of change from baseline was 49.6% (3.32/6/69) and in TARGET study (33) 47.4% (3.24/6.83).*

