
STATISTICAL CONSIDERATIONS
	
Sample size determination:
 
According to the literature and previous studies having assessed sarilumab, the standard deviation (SD) of the RAID score could be estimated at 2.5 points. On this basis, a sample size of 140 included patients in order to have at least 112 evaluable patients (assuming almost 20% of non-evaluable patients), produces a precision, two-sided 95% confidence interval (CI), with a distance from the mean to the limits that will be less than 0.5 (considering 20% non-evaluable patients) when the estimated SD is 2.5, assuming that the change from baseline will be from 30% to 50% of baseline score.
 
Analysis populations:
 
 
• Intent-to-treat (ITT) population: all patients who met the eligibility criteria and who are actually treated.
 
• Safety population: all patients who have signed the Informed Consent Form (ICF) and have been exposed to at least one dose or part of a dose of IMP.
 
• Per-protocol population: patients of ITT population without major protocol deviations.
 
 
Primary analysis:
 
The primary study objective is to assess the change in RAID score from baseline to W24.
 
The number of available data, mean, standard deviation, median and range (minimum, maximum) will be provided with the 95% confidence interval of the mean change from baseline to W24. Main analysis will be performed on ITT population. Sensitivity analysis will be conducted in reproducing the same analysis using the per-protocol population.
 
In addition, multivariate analyses such as ANCOVA, Logistic Regressions and Multiple Correspondences analysis can be performed from baseline in order to exploratory explain patient profiles.
 
Analysis of secondary endpoints:
 
All secondary parameters will be described; 95% CI will be provided.

DURATION OF STUDY PERIOD (per patient)	The total duration of the core study period per patient is expected to be approximately 32 weeks: 

• Up to 4-week screening

• 24 weeks treatment

• 2-4 week post-treatment observations.

 For patients who will enter in the LTE period, a maximum of another 24 weeks is planned.
---	--

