#### **11.4.2 Analyses of efficacy endpoints**

##### **11.4.2.1 Analysis of primary efficacy endpoint**

The primary study objective is to assess the change in RAID score from baseline to W24. The number of available data, mean, standard deviation, median and range (minimum, maximum) will be provided with the 95% confidence interval of mean change from baseline to W24. Main analysis will be done on ITT population. Sensitivity analysis will be conducted in reproducing the same analysis using the per-protocol population.

In addition, multivariate analyses such as ANCOVA (Analyze of Covariance), Logistic Regression and Multiple Correspondences analysis can be performed from baseline in order to exploratory explain different profiles of patients. The details of these analyses will be described on the statistical analyses plan before database frozen.

In case of any event mentioned below, the last available endpoint before the considered event will be taken in account (for RAID score for primary endpoint and for all other secondary endpoints):

- Lack of efficacy
  - More than one glucocorticoid infiltration per articulation
  - Dose increase of an ongoing glucocorticoid or start of systemic glucocorticoid treatment
  - Change in NSAID due to lack of efficacy or adverse event considered as related to treatment by the investigator
- Missing data
  - Treatment discontinuation due to lack of efficacy or adverse event (except for AEs due to NSAID). For all other cases, missing data will not be replaced.

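### Protocol 11.1 and SAP 1.4 give 122 evaluable patients and a precision of 0.44; 140 patients with 20% loss give 112 and 0.46 to 0.47, still under the 0.5 target.

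*Protocol*

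**What the plan says.** The trial is single-arm and descriptive, with no hypothesis test (Protocol 11.4.2.3). Its size is justified by the half-width of the two-sided 95% confidence interval for the mean change in RAID from baseline to week 24, which is to be below 0.5.

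- **Protocol 11.1 and SAP 1.4:** "a sample size of 140 patients (122 evaluable, if 20% non-evaluable patients) produces a precision" under 0.5 at an SD of 2.5.
- **Protocol synopsis, Statistical considerations:** "a sample size of 140 included patients in order to have at least 112 evaluable patients", with a loss of almost 20%.
- **Protocol 11.1, sentence before the table (also in SAP 1.4):** "Table below gives the 95% CI of change from baseline to W24 of RAID score with this precision (0.44".
- **Protocol 11.1, column header of that table:** "95% CI (precision =0.5".
- **Protocol 11.1, basis for the SD:** "the standard deviation (SD) of the RAID score could be estimated at 2.5 points".

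**The concern.** The same 140 patients and the same loss of about 20% give 112 evaluable patients in the synopsis and 122 in Protocol 11.1 and SAP 1.4. Precision is 0.44 in the text that introduces the table and 0.5 in the table's header. The half-width is the only sample-size criterion, so a reader who compares the achieved evaluable number and interval width with the plan cannot tell which planned figures apply. The SAP already carries 122 and 0.44, and the study report could take them from there.

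A second, weaker point is that the SD is described as that of the RAID score but is applied to the change from baseline. The two need not be equal.

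**Working it through.** **Inputs.** N = 140, loss 20%, SD 2.5, two-sided 95%, target half-width below 0.5 (Protocol 11.1, SAP 1.4).

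**1. Evaluable patients.**
- 140 × (1 − 0.20) = 112, as in the synopsis.
- 122/140 = 0.871, a loss of 12.9%.
- Dividing by 1.2 gives 140/1.2 = 116.7, not 122.
- Keeping 122 after a 20% loss would need 122/0.80 = 152.5, so 153 enrolled.

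None of these turns 140 and 20% into 122. The documents do not say where 122 came from.

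**2. The plan's own precision.** Half-width = quantile × SD/√n.

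| n | normal quantile | t quantile |
|---|---|---|
| 122 | 1.96 × 2.5/√122 = 0.4436 | 0.448 |
| 112 | 1.96 × 2.5/√112 = 0.4630 | 0.468 |
| 140 | 0.414 | 0.418 |

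Of these, only n = 122 with the normal quantile rounds to 0.44, so the wrong count produced the second wrong figure. On the same quantile the correct half-width is √(122/112) = 1.044 times as large, or 4.4% wider.

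**3. Does the target survive?** The smallest n with a half-width below 0.5 at SD 2.5 is 97 (normal, 0.4975) or 99 (t, 0.4986). With 99, the tolerable loss is (140 − 99)/140 = 29.3%. Also, 112/0.80 = 140, so enrolment is right for 112 evaluable patients.

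**4. The table in Protocol 11.1.** The printed changes are 2.0, 1.5, 1.1, 3.3, 2.5 and 1.8.
- With ±0.44 they give [1.6; 2.4], [1.1; 1.9], [0.7; 1.5], [2.9; 3.7], [2.1; 2.9] and [1.4; 2.2]. None matches the printed intervals.
- With ±0.463, ±0.468 or ±0.5, all six match after rounding to one decimal.

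The table therefore follows its header, not the sentence that introduces it.

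**5. Which SD (lower confidence).** At n = 112, a half-width of 0.5 for the unadjusted mean change corresponds to an SD of the change of 0.5 × √112/1.96 = 2.70 (normal) or 2.67 (t). Assume, since the documents do not say, that 2.5 is the SD of the score at both visits. Then the SD of the change is 2.5 × √(2(1 − ρ)), where ρ is the correlation between baseline and week 24. The target then requires ρ ≥ 1 − (2.70/2.5)²/2 = 0.42 (normal) or 1 − (2.67/2.5)²/2 = 0.43 (t). The documents give no ρ, so a range is shown, with half-widths from the normal quantile at n = 112:

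| ρ | SD of change | half-width |
|---|---|---|
| 0.3 | 2.5 × √1.4 = 2.96 | 1.96 × 2.96/√112 = 0.55 |
| 0.5 | 2.5 × √1.0 = 2.50 | 1.96 × 2.50/√112 = 0.46 |
| 0.7 | 2.5 × √0.6 = 1.94 | 1.96 × 1.94/√112 = 0.36 |

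This concerns the simple mean change, which Protocol 11.4.2.1 says "will be provided with the 95% confidence interval of mean change from baseline to W24". It does not carry over to the baseline-adjusted model in SAP 5.3.2.2. There, under the same assumption, the residual SD is 2.5 × √(1 − ρ²), which never exceeds 2.5.

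**The case against.** The strongest reply is that nothing depends on the wrong figures. The operative criterion in all three places is a half-width below 0.5, which is true at 112 and at 122. The correct count is already in the synopsis, and the trial will report its observed interval whatever was planned. That stands: there is no design consequence, only an error of record.

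The table check can also be challenged. It uses the printed, rounded changes. If one starts instead from the unrounded products (30% or 50% of baseline, reading the first row's baseline as 6.5), 1.95, 1.05, 3.25 and 1.75 plus 0.463 give upper limits of 2.4, 1.5, 3.7 and 2.2, against 2.5, 1.6, 3.8 and 2.3 as printed. Only 0.5 fits both ways. This is correct, and it supports reading the column as the ±0.5 bound. It does not rescue 0.44, which matches no row by either route.

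On the SD, Protocol 11.1 also cites two sarilumab trials and reports mean changes from them, so 2.5 may already be the SD of a change. The documents do not settle this, so the point can only be a request for confirmation.

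Finally, Protocol 15 requires ethics committee approval before an amendment is implemented, so a protocol edit for this alone would be out of proportion. That stands too, and it affects the route of the correction.

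**Conclusion.** The concern holds. With the plan's own inputs, the evaluable number is 112, not 122, and the half-width is 0.46 (normal) or 0.47 (t), not 0.44. Confidence is high, because this rests only on figures printed in the documents. At SD 2.5, N = 140 and the target below 0.5 both stand, with room for about 29% loss. The correction should be made, but its consequence is limited to the accuracy of the record.

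The SD question is low to moderate in confidence. No error is shown. If 2.5 is the SD of the score and not of the change, the target for the unadjusted mean depends on a correlation that the documents do not give.

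**What to change.** - In SAP 1.4, replace 122 with 112, and replace 0.44 with 0.46 (normal quantile, as used for 0.44) or 0.47 (t), stating which. Record the correction in SAP 1.6 as a change from the protocol.
- Make the same two changes in Protocol 11.1 when it is next amended. Label the ±0.5 in its table as the upper bound on the half-width. The printed intervals need no change.
- Separately, check in the cited sources whether 2.5 is the SD of the change, and cite the source used. If only an SD of the score is available, say so, and state that at 112 patients the target for the unadjusted mean change holds up to an SD of the change of about 2.67.

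The cost is a few words in two sections and one check of references. Enrolment and analysis do not change. The stated precision becomes slightly less favourable.
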